Confidential

	In order to calculate the sample size for the study, initially a requirement was chosen that the length of the 95% confidence interval of the mean change from baseline to 4h does not exceed 0.2 mmol/L at an observed historical standard deviation of 0.3. With a targeted minimum of 25 subjects evaluable for this endpoint, the length of this confidence interval is maintained with a slight increase to 0.25 mmol/L. The safety data analysis will be presented with special focus on LysaKare [®] related treatment emergent events and will be applied to the full Safety Set. Changes in Vital Signs and ECG will be summarized by time. Changes in laboratory parameters (Haematology and Blood Chemistry) will be described by time.
Key words	LysaKare [®] , amino acid, GEP-NET, PRRT, Lutathera [®]

Advanced Accelerator Applications Clinical Trial Protocol (Version 01)

Confidential

Version history

Version Number	Description
Global protocol v00 dated 12-Nov-2019	Initial global protocol. Approved in all countries.
Local protocol v00 PL.01 dated 18-May-2021	Local amended protocol from v00. Approved in Poland
Global protocol v01 dated 01-Dec-2022	Amended global protocol from v00 and local protocol v00-PL.01 dated 18-May-2021

Protocol Amendment 01

As of 08 November 2022, 30 patients were enrolled into the study and received an infusion of LysaKare[®].

Amendment rationale

The primary purpose of this amendment is to provide clarification on the sampling requirements for laboratory assessments. The Sponsor identified discrepancies in sampling used for electrolytes which were not performed as per protocol requested procedures. This resulted in samples collected with heparinized blood (2 patients) and whole blood (11 patients) instead of serum sampling across 4 sites. Therefore, the Visit Schedule and assessments in Section 8 have been updated to clarify the requirements of laboratory assessments.

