12.5.1 Safety endpoints

Adverse events

All information obtained on adverse events will be displayed for the Safety set and by subject.

The number (and percentage) of subjects with treatment emergent adverse events (events started after the first dose of study medication or events present prior to start of treatment but increased in severity based on preferred term) will be summarized in the following ways:

- by primary system organ class and preferred term.
- by primary system organ class, preferred term and maximum severity.

• by Standardized MedDRA Query (SMQ) and preferred term

Separate summaries will be provided for study medication related adverse events, death, serious adverse events, other significant adverse events leading to discontinuation and adverse events leading to dose adjustment.

The number (and proportion) of subjects with adverse events of special interest/related to identified and potential risks (see Section 10.1) will be summarized.

A subject with multiple adverse events within a primary system organ class is only counted once towards the total of the primary system organ class.

Vital signs

All vital signs data will be listed by subject, and time and if ranges are available, abnormalities (and relevant orthostatic changes) will be flagged. Summary statistics will be provided by time.

12-lead ECG

PR, QRS, QT, QTcF, and RR intervals will be obtained from 12-lead ECGs for each subject during the study. ECG data will be read and interpreted locally. The ECG parameters will be summarized by time.

Clinical laboratory evaluations

All laboratory data will be listed by subject, and visit/time and if normal ranges are available abnormalities will be flagged. Summary statistics will be provided by treatment and time. Shift tables using the low/normal/high/ (low and high) classification will be used to compare baseline to the worst on-treatment value.

Grading of laboratory values will be assigned programmatically as per NCI Common Terminology Criteria for Adverse Events (CTCAE) version 5.0 or current version. The calculation of CTCAE grades will be based on the observed laboratory values only, clinical assessments will not be taken into account.

CTCAE Grade 0 will be assigned for all non-missing values not graded as 1 or higher. Grade 5 will not be used.

For laboratory tests where grades are not defined by CTCAE, results will be categorized as low/normal/high based on laboratory normal ranges.

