1.2 Study objectives, endpoints and estimands

safety profile

Objectives and related endpoints are described in Table 1-1 below.

Table 1-1Objectives and related endpoints

Objectives	Endpoints	
Primary objective	Endpoint for primary objective	
To assess the effect of LysaKare® administration on serum potassium concentration in GEP-NET patients eligible for Lutathera® treatment	Change in serum potassium levels at specified time points after LysaKare [®] Intravenous (IV) administration compared to baseline.	
Secondary objective	Endpoints for secondary objective(s)	
To characterize the safety profile on LysaKare [®] infusion in GEP-NET patients eligible for Lutathera [®] treatment without co-administration of Lutathera [®]	 Incidence of LysaKare[®] related AEs Changes in vital signs and Electrocardiogram (ECG) parameters Change in laboratory parameters 	

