2.7.3 Laboratory data

On analyzing laboratory data, data from all sources will be combined. The summaries will include all assessments available for the lab parameters collected no later than 24 hours after the start of the LysaKare[®] infusion. The laboratory parameters that will be investigated, and the timing that the laboratory parameters will be assessed are summarized in Table 2-1.

	ematology and Chemist		incitta
Haematology (Assessment at screening, pre-dose and 24h after start of the infusion)	Blood Chemistry (serum) (Assessment at screening, pre-dose and 24h after start of the infusion)	Electrolytes (serum) (Assessment at screening, pre-dose and 2h, 4h, 6h, 8h, 12h and 24h after start of the infusion)	Venous Blood Gas (Assessment at screening, pre-dose and 2h, 4h, 6h, 8h, 12h and 24h after start of the infusion)
WBC with differential	BUN or urea	Potassium	рН
Platelets	Uric acid	Sodium	Lactate
Haemoglobin	Serum creatinine	Chloride	pCO2
Haematocrit	Creatinine clearance* Albumin Total bilirubin Alkaline phosphatases AST/ASAT ALT/ALAT	HCO3	
	Gamma-GT		
	Glucose		
	LDH		

Table 2-1 Hematology and Chemistry Laboratory Assessments

(*) Calculated using Cockcroft-Gault formula

Laboratory values outside normal ranges will be listed and flagged. The following flags will be used:

'+': 'Higher than reference value'

'-': 'Lower than reference value'

The respective parameter and the flagged value will be presented patient-wise by visit together with the reference values.

Advanced Accelerator Applications,	Confidential	Page 19 of 27
A Novartis company		
SAP amendment		CAAA001A12401

The following summaries will be produced for hematology and biochemistry laboratory data (by laboratory parameter and treatment):

- Worst post-baseline Common Toxicity Criteria (CTC) grade (regardless of the baseline status). Each subject will be counted only for the worst grade observed post-baseline.
- Shift tables using CTC grades to compare baseline to the worst on-treatment value.
- For laboratory tests where CTC grades are not defined, shift tables using the low/normal/high/(low and high) classification to compare baseline to the worst on-treatment value.

The following listings will be produced for the laboratory data:

- Listings of all laboratory data, with CTC grades and classification relative to the laboratory normal range. Lab data collected during the post-treatment period will be flagged.
- Listing of all CTC grade 3 or 4 laboratory toxicities.

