2.7.4.2 Vital signs

Physical examinations will be performed by the Investigator, or qualified designee. All body systems will be examined, and any relevant findings will be documented in the source documents and eCRF. Physical examinations should include weight measurement (height will only be measured at baseline). Vital signs measurements should include heart rate, blood pressure and respiratory rate, and will be performed after the patient rests for 5 minutes. For each patient, all blood pressure recordings shall be made using the same type of instrument (i.e., manual BP recording vs. automatic digital vital signs monitor) on the same arm.

Data handling

Vital signs collected on treatment will be summarized. Values measured outside of on treatment period will be flagged in the listings.

Data analysis

For analysis of vital signs, the clinically notable vital sign criteria are provided in Table 2-2 below.

Vital sign (unit)	Clinically notable criteria	
	Above normal value	Below normal value
Weight (kg)	increase > =10% from Baseline	decrease > 10% from Baseline
Systolic blood pressure (mmHg)	>=180 with increase from baseline of >=20	<=90 with decrease from baseline of >=20
Diastolic blood pressure (mmHg)	>=105 with increase from baseline of >=15	<=50 with decrease from baseline of >=15
Pulse rate (bpm)	>=100 with increase from baseline of >25%	<=50 with decrease from baseline of > 25%

Table 2-2Clinically notable changes in vital signs

The number and percentage of subjects with notable vital sign values (high/low) will be presented. Descriptive statistics will be tabulated for baseline, at each post-baseline time point and changes from baseline at each post-baseline time point for each vital sign measure.

A listing of all vital sign assessments will be produced, and notable values will be flagged. In the listing, the assessments collected outside of on-treatment period will be flagged.

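### SAP 2.7.3 specifies no numerical change over time for haematology or chemistry, although change in laboratory parameters is a secondary endpoint and the protocol says it will be described by time

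*SAP*

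**What the plan says.** **Endpoint.** Protocol Table 2-1 and SAP Table 1-1 both list "Change in laboratory parameters" as a secondary endpoint.

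**Protocol analysis.** The Data analysis part of the synopsis states: "Changes in laboratory parameters (Haematology and Blood Chemistry) will be described by time". Under Clinical laboratory evaluations, protocol 12.5.1 states: "Summary statistics will be provided by treatment and time". Its next sentence adds low/normal/high shift tables from baseline to the worst on-treatment value. The protocol therefore promises summary statistics by time and shift tables as two separate outputs.

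**SAP analysis.** SAP 2.7.3 opens its list with "The following summaries will be produced for hematology and biochemistry laboratory data (by laboratory parameter and treatment" and gives three items:
- "Worst post-baseline Common Toxicity Criteria (CTC) grade (regardless of the baseline status";
- "Shift tables using CTC grades to compare baseline to the worst on-treatment value";
- for tests without CTC grades, "shift tables using the low/normal/high/(low and high) classification to compare baseline to the worst on-treatment value".

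The liver parameters part of the same section adds counts of patients above multiples of the upper limit of normal. Listings of all laboratory data and of grade 3 or 4 values complete the section.

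**Other safety data.** For vital signs, SAP 2.7.4.2 says: "Descriptive statistics will be tabulated for baseline, at each post-baseline time point and changes from baseline" at each post-baseline time point. SAP 2.7.4.1 does the same for ECG. SAP 2.5.6 repeats the primary analysis for sodium, chloride, pH, lactate, CO2 and HCO3.

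**The concern.** Haematology and chemistry are the only scheduled laboratory groups for which the SAP plans no mean, median or change from baseline at a time point. The shift-table half of protocol 12.5.1 was carried into SAP 2.7.3. The half giving summary statistics by time was not, and SAP section 4, which is the place to record changes to protocol-specified analyses, covers only COVID-19.

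What is at stake is the aggregate size of change. A shift table registers a change only when a patient crosses a grade boundary or a normal limit. If most patients moved the same way at 24 h but stayed within category, the planned tables would show little or nothing. In a single-arm descriptive safety study, the size of such a movement is the natural way to report this endpoint.

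**Working it through.** The documents give no figure on this point to reproduce, so the main check compares texts.

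**1. Which outputs give a numerical change over time?**

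| Data | SAP section | Numerical change from baseline by time? |
|---|---|---|
| Serum potassium | 1.2.1, 2.5 | Yes |
| Sodium, chloride, HCO3, pH, lactate, CO2 | 2.5.6 | Yes (primary analysis repeated) |
| ECG | 2.7.4.1 | Yes |
| Vital signs | 2.7.4.2 | Yes |
| Haematology (4 lines in Table 2-1) | 2.7.3 | None specified |
| Chemistry (12 lines in Table 2-1) | 2.7.3 | None specified |

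The 4 haematology lines are WBC with differential, platelets, haemoglobin and haematocrit. The 12 chemistry lines are urea, uric acid, creatinine, creatinine clearance, albumin, total bilirubin, ALP, AST, ALT, gamma-GT, glucose and LDH. This counts table lines: the differential is one line, and creatinine clearance is derived from creatinine.

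**2. How much is needed to fill the gap?** Protocol Table 8-1 and SAP Table 2-1 schedule haematology and chemistry at screening, 0 h and 24 h. There is one scheduled post-dose value, so one contrast per parameter (0 h to 24 h) is enough.

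**3. What could a shift table miss?** This is an illustration under assumptions that are not in the documents: normally distributed values, a reference range of mean ± 1.96 SD, and the same upward shift of d SD in every patient. N = 45 is the approximate planned enrolment.

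Patients newly above the upper limit = 45 × [(1 − Φ(1.96 − d)) − (1 − Φ(1.96))].

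- d = 0.25: 45 × (0.0436 − 0.0250) = 0.8 patients.
- d = 0.50: 45 × (0.0721 − 0.0250) = 2.1 patients.

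The mean change, in contrast, has a 95% CI half-width of t(0.975, n − 1)/√n, in units of the SD of the change:

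- n = 45: 0.30 SD.
- n = 38: 0.33 SD.

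The two SD units differ. The first is the spread between patients; the second is the spread of the within-patient change. With equal variances and correlation r between 0 h and 24 h, SD of change = SD × √(2(1 − r)). The two are equal at r = 0.5, and the SD of change is smaller when r is higher. The documents give no SD or correlation for any of these parameters, so this shows how the two outputs behave and predicts nothing for a particular test.

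**4. Would a 24 h table include all the 24 h samples?** SAP 2.7.3 limits laboratory summaries to assessments no later than 24 hours after the start of infusion. Protocol 8.4.2 and SAP 2.1.1 accept the 24 h assessment within ± 2 hours, that is from 22 h to 26 h. SAP 2.1.1 adds that even out-of-window assessments are still analysed. Read literally, 2.7.3 would exclude a valid sample taken between 24 h and 26 h, which is the only scheduled post-dose haematology and chemistry value for that patient.

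**The case against.** A reader might infer that this secondary endpoint goes unanalysed, or that the sponsor deliberately dropped the analysis. The documents support neither.

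- **The shift tables do compare baseline with post-dose.** With one scheduled post-dose sample, the worst value is normally the 24 h value, so they amount to a categorical 0 h to 24 h comparison. What is missing is the numerical summary. This stands.
- **The SAP's list does not say that nothing else will be produced.** SAP 2.1.1 time-slots laboratory data so that they can be summarised over time, and mentions change-from-baseline summaries where appropriate. SAP 2.1 says quantitative data get descriptive statistics. This suggests an unlisted output rather than a decision to omit one. None of these conventions names a laboratory table, parameter or time point, however, and the SAP did not rely on them for ECG or vital signs.
- **The protocol wording leaves some room.** Section 12.5.1 promises summary statistics by time without mentioning change. Only the synopsis promises change by time, and it names no statistic. Mean change with SD is a reasonable reading, but not a stated requirement.
- **A marked change would not go unseen.** All values are listed, liver elevations are counted, and the liver text defines a baseline-relative signal for patients with abnormal ALT or AST at baseline. Protocol 8.4.2 sends clinically relevant changes to the adverse event page, and 10.1.1 counts significant change from baseline among the ways to identify a notable result. This stands: only the aggregate size of change is missing. Listings and event reports do not supply it.
- **The study is descriptive and potassium is primary.** This is correct, and it sets the severity.

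**Conclusion.** The gap is real and narrow. Following the list in SAP 2.7.3 gives no aggregate numerical change for any of the 16 haematology and chemistry lines in SAP Table 2-1, although the endpoint is named in both documents and the protocol synopsis says these changes will be described by time. No departure is declared in SAP section 4.

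The conclusion rests on the text alone and needs no assumption about effect size. The illustration, in which a shift of 0.25 to 0.5 SD moves about 0.8 to 2.1 of 45 patients across a limit, depends on its stated assumptions. It shows only why categories are a poor substitute for a mean. Nothing in the documents indicates that such a shift is expected.

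Severity is low. One descriptive table is missing, and the primary potassium result does not depend on it.

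**What to change.** Add one item to the list in SAP 2.7.3: for each haematology and chemistry parameter, on the Safety Set, descriptive statistics (N, mean, SD, median, quartiles, minimum, maximum) at baseline, at 24 h and for the change from baseline to 24 h. Values should be in common units across the local laboratories; SAP 5.3 already refers to SI conversion. If the omission is intended, declare and justify it in SAP section 4 instead.

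In the same edit, reconcile the 24-hour limit in SAP 2.7.3 with the window of ± 2 hours and the out-of-window rule in SAP 2.1.1. One way is to admit the scheduled 24 h assessment by its nominal time point.

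The cost is one standard output from data already collected at 0 h and 24 h. The table carries out what the protocol already says, so no protocol amendment is needed.

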2.7.4 Other safety data

2.7.4.1 ECG data

Single standard 12-lead ECGs will be obtained using an ECG machine that automatically calculates heart rate (HR) and measures RR, PR, QRS, QT, and QTcF intervals. All ECG

Advanced Accelerator Applications,	Confidential	Page 20 of 27
A Novartis company		
SAP amendment		CAAA001A12401

assessments will be performed in the supine position. All ECG assessments will be read and interpreted locally. ECGs will be reported at screening, and at the 0h (before LysaKare[®] injection) as well as the 4h, 8h, and 24h timepoints (after LysaKare[®] injection).

Data handling

In case of ECG replicates at any assessment, the average of the ECG parameters at that assessment should be used in the analyses.

Data analysis

The number and percentage of subjects with notable ECG values will be presented.

- QT, QTcF
 - New value of > 450 and ≤ 480 ms
 - New value of > 480 and ≤ 500 ms
 - New value of > 500 ms
 - Increase from Baseline of > 30 ms to ≤ 60 ms
 - Increase from Baseline of > 60 ms
- HR
 - Increase from baseline >25% and to a value >100 bpm
 - Decrease from baseline >25% and to a value < 50 bpm
- PR
 - Increase from baseline >25% and to a value >200 ms
 - New value of > 200 ms
- QRS
 - Increase from baseline >25% and to a value > 120 ms
 - New values of QRS > 120 ms

The summaries will include all ECG assessments performed no later than 30 days after the last study treatment date.

A listing of all ECG assessments will be produced and notable (e.g. clinically significant abnormality) values will be flagged. In the listing, the assessments collected during the post-treatment period will be flagged.

For each of the ECG parameters, descriptive statistics at baseline, at each post-baseline time point and changes from baseline at each post-baseline time point will be summarized. Changes from baseline to maximum for QTcF will also be summarized.

Patients with notable ECG interval values will be listed and the corresponding notable values and abnormality findings will be included in the listings.

Unscheduled ECG measurements will not be used in computing the descriptive statistics for change from baseline at each post-baseline time point. However, they will be used in the analysis of notable ECG values.

Advanced Accelerator Applications,	Confidential	Page 21 of 27
A Novartis company		
SAP amendment		CAAA001A12401

2.7.4.2 Vital signs

Physical examinations will be performed by the Investigator, or qualified designee. All body systems will be examined, and any relevant findings will be documented in the source documents and eCRF. Physical examinations should include weight measurement (height will only be measured at baseline). Vital signs measurements should include heart rate, blood pressure and respiratory rate, and will be performed after the patient rests for 5 minutes. For each patient, all blood pressure recordings shall be made using the same type of instrument (i.e., manual BP recording vs. automatic digital vital signs monitor) on the same arm.

Data handling

Vital signs collected on treatment will be summarized. Values measured outside of on treatment period will be flagged in the listings.

Data analysis

For analysis of vital signs, the clinically notable vital sign criteria are provided in Table 2-2 below.

Vital sign (unit)	Clinically notable criteria	
	Above normal value	Below normal value
Weight (kg)	increase > =10% from Baseline	decrease > 10% from Baseline
Systolic blood pressure (mmHg)	>=180 with increase from baseline of >=20	<=90 with decrease from baseline of >=20
Diastolic blood pressure (mmHg)	>=105 with increase from baseline of >=15	<=50 with decrease from baseline of >=15
Pulse rate (bpm)	>=100 with increase from baseline of >25%	<=50 with decrease from baseline of > 25%

Table 2-2Clinically notable changes in vital signs

The number and percentage of subjects with notable vital sign values (high/low) will be presented. Descriptive statistics will be tabulated for baseline, at each post-baseline time point and changes from baseline at each post-baseline time point for each vital sign measure.

A listing of all vital sign assessments will be produced, and notable values will be flagged. In the listing, the assessments collected outside of on-treatment period will be flagged.

2.8 Pharmacokinetic endpoints

Not applicable.

2.9 PD and PK/PD analyses

Not applicable.

2.10 Patient-reported outcomes

Not applicable.

Advanced Accelerator Applications, A Novartis company SAP amendment Confidential

Page 22 of 27

2.11 Biomarkers

Not applicable.

2.12 Other Exploratory analyses

Not applicable.

2.13 Interim analysis

Not applicable.

3 Sample size calculation

The primary endpoint is the change in serum potassium levels after LysaKare® IV administration compared to baseline. In a previous study, which assessed hourly potassium changes in 11 patients treated with LysaKare®, peak concentration was observed at 2-4 h post-baseline, the mean baseline level was 4.2 mmol/L, mean increase at 2 h was 0.6 mmol/L and at 4 h it was 0.9 mmol/L (SD=0.3); the maximum increase was 1.5 mmol/L (Krenning et al., 2000). The mild increase in potassium levels did not manifest in any safety issues or clinically significant events. Since the maximum mean increase was observed at 4h, sample size calculations were based on the expected mean change in serum potassium levels at the 4h timepoint.

The current study will describe the expected mean change at 4h by a point estimate and the corresponding 95% confidence interval. In historical data a mean increase from baseline to 4h of 0.9 mmol/L was observed with a standard deviation of 0.3.

The criterion for choice of sample size will be based on length of confidence interval of the mean change at 4h calculated using the t-distribution. A requirement was initially chosen that the confidence interval has a total length not exceeding 0.2 mmol/L assuming the historical standard deviation to be valid, i.e. the distance should be no more than 0.1 mmol/L from the mean to the limit of the confidence interval when the estimated standard deviation is 0.3.

The initially estimated sample size of 38 subjects produces a two-sided 95% confidence interval with a distance from the mean to the limits that is equal to 0.099 when the estimated standard deviation is 0.3. With the required minimum number of 25 evaluable subjects for the primary endpoint analysis, the confidence interval total length is maintained with a slight increase to 0.25 mmol/L.

Additionally, the originally estimated sample size of 38 implies an adequate probability of observing common and very common AEs, see Table 3-1 below. This estimate holds true because the current laboratory sampling issue only impacts the evaluable number for the primary endpoint. Other safety assessments based on AEs remain evaluable for the whole safety set.

Advanced Accelerator Applications,	Confidential	Page 23 of 27
A Novartis company		
SAP amendment		CAAA001A12401

Table 3-1Likelihood of observing at least one case for given sample size and
incidence.

Sample size	Incidence of Adverse	e Event	
	5%	10%	
10	0.401	0.651	
20	0.642	0.878	
30	0.785	0.958	
38	0.858	0.982	
40	0.871	0.985	

The table displays the probability of observing at least one case of a certain AE which has the incidence of 5% or 10% in this patient population for the sample sizes of 10, 20, 30, 38, and 40. Any further increase in total sample size ensures that this probability remains above 87%.

Since the sample size of 38 assumes no drop-out, additional subjects have been added to hedge against drop-out. Given the design of the study, no or very minor drop-out is expected. The additional precaution is taken to ensure at least 25 subjects are evaluable for the primary endpoint analysis as discussed in the amendment rationale. Therefore, the adjusted sample size is approximately 45 subjects.

4 Change to protocol specified analyses.

